7.9 End of Trial

End of Trial is defined as last patient's last visit or death. "Date of trial completion" is the date the patient completed the final scheduled visit.

7.10 Number of Patients

With an estimated screen failure rate of 25% approximately 70 patients will be screened to achieve the planned 52 patients.

7.11 Patient Selection

The trial will include patients with high-risk NB who have received SoC frontline chemotherapy with or without autologous stem cell transplant (ASCT) and have been designated primary refractory disease or have experienced first relapse following frontline SoC, comparable to the following protocols for frontline therapy:

- Childrens Oncology Group (COG) protocol 0532,
- COG-US protocol A3973
- GPOH based induction (as per the NB 2004)
- MSKCC N5 or N7 (MSK-US)
- Rapid Cojec (SIOPEN)

To be eligible, the patient must meet all inclusion criteria and must not violate any of the exclusion criteria. Patient eligibility must be approved by the sponsor before the patient receives IMP in the trial. This is done by completing the patient eligibility form.

7.11.1 Inclusion Criteria

1. Documented NB at time of initial diagnosis³⁶ defined as:
 - Histopathological verification of NB or ganglioneuroblastoma nodular, or
 - BM aspirate or biopsy indicative of NB (according to INRC)³⁷ and high blood or urine catecholamine metabolite levels (> 2 x upper limit of normal)
2. Documented high-risk disease at time of initial diagnosis defined as^{33, 38}:
 - MYCN-amplified any stage (according to International Neuroblastoma Risk Group (INRG)) of any age or
 - MYCN-nonamplified with stage M (according to INRG) and diagnosed at \geq 18 months of age
3. Patient should have received SoC frontline induction/consolidation therapy (surgery, chemotherapy, ASCT, MIBG, radiotherapy, immunotherapy, or retinoids)
4. Patients must have active disease despite previous aggressive multi-drug chemotherapy (\geq 2 agents, including an alkylating agent and a platinum containing compound) defined as one of the following:
 - verified first progression during multi-drug frontline treatment or
 - verified first episode of relapse, defined as recurrence after response to frontline treatment, or
 - verified first designation of refractory disease, defined as persistent metastatic disease (SD or minor response by INRC^{37, 39} and MIBG curie score \geq 3³⁹) detected at conclusion of at least 4 cycles of multi-drug induction chemotherapy on or according to a high-risk NB treatment protocol as defined above (7.11).
5. The patients must have one of the following (locally assessed) obtained within 3 weeks prior to enrollment and at least 10 calendar days after end of any prior anti-cancer treatment:
 - Measurable tumor on CT/MRI scan that is MIBG-avid or demonstrates increased FDG uptake on PET scan
 - MIBG scan with positive uptake at a minimum of one site. This site must represent disease recurrence after completion of therapy, progressive disease on therapy, or refractory disease during induction
6. Aged \geq 12 months at enrollment
7. Written informed consent from legal guardian(s) and/or patient obtained in accordance with local regulations. Pediatric patients must provide assent as required by local regulations

7.11.2 Exclusion Criteria

1. A diagnosis of myelodysplastic syndrome or any malignancy other than NB
2. Any systemic anti-cancer therapy, including chemotherapy, or immunotherapy, within 3 weeks prior to enrollment
3. ASCT within 6 weeks prior to enrollment or ongoing toxicity due to the stem cell transplant at the discretion of the investigator
4. Therapeutic ¹³¹I-MIBG within 6 weeks prior to enrollment
5. RT within 4 weeks prior to enrollment at the site of any lesion that will be identified as a target lesion to measure tumor response. Lesions that have been previously radiated cannot be used as target lesions unless there is radiographic evidence of progression at the site following radiation or a biopsy done following radiation shows viable NB. There are no time restrictions following prior RT for non-target lesions or for palliative radiation to sites that will not be used for response assessment
6. Prior treatment with anti-GD2 therapy if the patient experienced PD while on anti-GD2 treatment
7. Receipt of second line chemotherapy after designation of primary refractory disease or first relapse or PD
8. Patients with NB in BM only
9. NB in the CNS or leptomeningeal disease within 6 months prior to enrollment
10. Performance status of < 50% as per the Lansky scale (patients less than 16 years of age) or Karnofsky scale (for patients aged 16 years or older)
11. Life expectancy of less than 6 months, as judged by the Investigator
12. Left ventricular ejection fraction < 50% by echocardiography
13. Inadequate pulmonary function defined as evidence of dyspnea at rest, exercise intolerance, and/or chronic oxygen requirement. In addition, room air pulse oximetry < 94% and/or abnormal pulmonary function tests if these assessments are clinically indicated
14. Patients with \geq Grade 2 diarrhea
15. Treatment with long-acting myeloid growth factor within 14 days or short-acting myeloid growth factor within 7 days prior to first dose of GM-CSF
16. Treatment with immunosuppressive treatment (local steroids excluded) within 4 weeks prior to enrollment
17. Life threatening infection(s)
18. Patients with uncontrolled seizure disorders despite anticonvulsant therapy (defined as a seizure event within 3 months prior to enrollment)
19. Treatment with enzyme-inducing anticonvulsants including phenytoin, phenobarbital, or carbamazepine for at least 7 days prior to enrollment
20. Concomitant use with St John's wort

21. Allogeneic hematopoietic stem cell transplantation (allo-SCT) or donor-lymphocyte-infusion (defined as any kind of active allogeneic lymphocyte suspension)
 - a. within 6 months of 1st dose of GM-CSF or
 - b. with a lymphocyte count $< 0.2 \times 10^9/L$
22. Treatment with Hematopoietic Progenitor Cell (HPC) boost within 2 months prior to enrollment
23. History of allergy or known hypersensitivity to GM-CSF, yeast-derived products, or any component of GM-CSF, naxitamab, irinotecan or temozolomide
24. History of anaphylactic reactions CTCAE Grade 4 related to prior anti-GD2 antibody therapy
25. Unacceptable hematological status at screening (hematological support is allowed if administered ≥ 1 week before screening procedure), defined as one of the following:
 - a. Hemoglobin $< 5.0 \text{ mmol/L} (< 8 \text{ g/dL})$
 - b. White blood cell count $< 1000/\mu\text{L}$
 - c. Absolute neutrophil count $< 750/\mu\text{L}$
 - d. Platelet count $< 75,000/\mu\text{L}$
26. Unacceptable liver function at screening, defined as one of the following:
 - a. Alanine aminotransferase (ALT) and aspartate aminotransferase (AST) > 5 times upper normal limit (UNL)
 - b. Total bilirubin $> 1.5 \times \text{UNL}$
27. Unacceptable kidney function at screening, defined as:
 - Estimated glomerular filtration rate (eGFR) $< 60 \text{ mL/min}/1.73 \text{ m}^2$ calculated by the 2009 revised Bedside Schwartz Equation ([Appendix 1](#))
28. Inability to comply with protocol
29. Patients with a significant intercurrent illness (any ongoing serious medical problem unrelated to cancer or its treatment) that is not covered by the detailed exclusion criteria and that is expected to interfere with the action of IMPs or to significantly increase the severity of the toxicities experienced from trial treatment
30. Females of childbearing potential (as defined in Section [9.2.8](#)) who are pregnant, breast feeding, intend to become pregnant, or are not using adequate contraceptive methods as defined in [9.2.8](#) or males who are not using adequate contraceptive methods as defined in [9.2.8](#). Contraception must be used for 6 months after last IT treatment or 42 days after last naxitamab treatment whichever comes last for both genders

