7.12 Premature Discontinuation of Treatment

General discontinuation criteria

A patient should be discontinued from treatment with all IMPs if any of the following situations occur:

1. Grade 4 anaphylaxis related to naxitamab
2. Grade 3 anaphylaxis related to naxitamab not responding to medical intervention at the discretion of the investigator
3. Grade 4 sensory neuropathy or Grade 3 sensory neuropathy that interferes with daily activities for more than 2 weeks at the discretion of the investigator
4. CTCAE Grade 3 pain unresponsive to maximum supportive measures at the discretion of the investigator
5. Grade 4 bronchospasm
6. Grade 3 bronchospasm not responding to medical intervention at the discretion of the investigator
7. Posterior reversible encephalopathy syndrome (PRES)
8. The investigator judges it necessary for medical reasons/non-compliance
9. The patient receives prohibited therapy and/or procedures during the trial, see Section [8.4.8](#)
10. Pregnancy
11. Patient/legal guardian withdraw consent to treatment
12. PD

Discontinuation criteria for IT

A patient should be discontinued from IT treatment if any of the following situations occur:

1. If the patient experiences neutropenia that causes a delay \geq 14 days after the first dose reduction by 20% of irinotecan and the second dose reduction by 20% of temozolomide
2. If the patient experiences thrombocytopenia that causes a delay \geq 14 days after the first dose reduction by 20% of irinotecan and the second dose reduction by 20% of temozolomide
3. If the patient does not meet the criteria to start the next cycle within 21 days after the planned subsequent cycle start date
4. Recurrence of \geq Grade 3 diarrhea despite maximal use of anti-diarrheals, prophylactic antibiotics, and a dose reductions of irinotecan of 20%
5. Recurrence of \geq Grade 3 regimen-related nausea and/or vomiting despite optimization of anti-emetic drugs and a dose reduction of IT by 20%
6. If \geq Grade 3 regimen-related dehydration recurs and persists for >3 days despite a dose reduction of IT by 20%

Discontinuation criteria for GM-CSF

A patient should be discontinued from GM-CSF treatment if any of the following situations occur:

1. Injection site reactions \geq CTCAE Grade 3
2. Allergic reactions (including anaphylactic reactions) \geq CTCAE Grade 3

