8.1.1 Administration of IMP for Each Patient

The patient must have a well-functioning intravenous catheter before initiating any treatments for IV administration; a central line is recommended. For naxitamab treatment, site should have emergency equipment readily available, and the patient should have 2 well-functioning IV accesses before any naxitamab treatment is initiated.

Please refer to the IMP manual for more details on preparation and administration of temozolomide, irinotecan, GM-CSF and naxitamab.

Before administration of IMPs, patients must meet hematologic, renal and hepatic eligibility criteria for trial entry at the start of each treatment cycle (see Section [7.11.2](#)).

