8.1.3 Treatment delays and missed dosing

Minor adjustment of the treatment schedule due to medical circumstances (e.g., infection) at the discretion of the investigator or non-medical circumstances (e.g., public holidays) is allowed.

It is allowed to postpone the start of a new cycle due to IT toxicity for up to 21 days after the planned subsequent cycle start date (i.e., < 3-weeks delay in start of next cycle) (please see treatment discontinuation criteria Section [7.12](#)).

If a naxitamab dose is missed, administer the missed dose on Day 12. In that case, treatment with GM-CSF at 250 µg/m²/day should be continued until Day 12 (i.e., treatment from Day 6 to Day 12). Please refer to [Appendix 2](#) if the patient has discontinued IT treatment due to toxicity.

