8.4.4 Management of selected IT adverse reactions

8.4.4.1 Management of hematologic toxicities

Patients who experienced hematologic toxicity should receive dose-reduction of IT treatment as described in the following sections at the discretion of the investigator.

Dose-limiting neutropenia

Patients who experience neutropenia (absolute count $<750/\mu\text{L}$) that causes a delay of ≥ 14 days between treatment cycles in the absence of other toxicity requiring dose modification, should have the temozolomide dose reduced by 20% for subsequent cycles (i.e., 80 mg/m²/day see dose reduction nomogram in [Appendix 4](#)). If despite this 20% dose reduction neutropenia (absolute count $<750/\mu\text{L}$) recurs, causing a delay of ≥ 14 days between treatment cycles, reduce the irinotecan dose by 20% (i.e., irinotecan dose 40.0 mg/m²/day) and temozolomide dose by additional 20% (i.e., 60 mg/m²/day see dose reduction nomogram in [Appendix 5](#)) for subsequent cycles. For neutropenia requiring discontinuation of IT (please refer to Section [7.12](#)).

Dose-limiting thrombocytopenia

For patients who experience thrombocytopenia ($<75,000/\mu\text{L}$) that causes a delay of ≥ 14 days between treatment cycles with or without other hematologic toxicities, the dose of temozolomide should be reduced by 20% for subsequent cycles (i.e., 80 mg/m²/day see dose reduction nomogram in [Appendix 4](#)). If despite this 20% dose reduction, thrombocytopenia ($<75,000/\mu\text{L}$) recurs causing a delay of ≥ 14 days between treatment cycles, reduce the irinotecan dose by 20% (i.e., irinotecan dose 40.0 mg/m²/day) and temozolomide dose by additional 20% (i.e., 60 mg/m²/day see dose reduction nomogram in [Appendix 5](#)) for subsequent cycles. For thrombocytopenia requiring discontinuation of IT (please refer to Section [7.12](#)).

Delayed recovery of platelets, neutrophils, hepatic and/or renal laboratory parameters

Patients who do not meet laboratory criteria to start the next treatment cycle (see eligibility criteria Section [7.11.2](#)) within 21 days after the planned subsequent cycle start date (i.e., there is a ≥ 3 -week delay in start of next cycle) must be discontinued from IT.

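### Exclusion 26a joins ALT and AST with 'and', so read literally a rise in one enzyme alone requires no exclusion, cycle hold or IT stop

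*Combined protocol and SAP*

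**What the plan says.** Item 26 of the exclusion criteria (Section 7.11.2) lists two ways for liver function to be unacceptable at screening, and either is enough. Item (a) is "Alanine aminotransferase (ALT) and aspartate aminotransferase (AST) > 5 times upper normal limit (UNL"). Item (b) is total bilirubin above 1.5 × UNL.

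The rule is used again after screening:

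- Section 8.1.1 states that "patients must meet hematologic, renal and hepatic eligibility criteria for trial entry at the start of each treatment cycle", with a reference back to Section 7.11.2.
- Section 8.4.4.1 has a rule headed "Delayed recovery of platelets, neutrophils, hepatic and/or renal laboratory parameters". It begins "Patients who do not meet laboratory criteria to start the next treatment cycle (see eligibility criteria Section" 7.11.2) and requires IT to be discontinued when the delay reaches three weeks.
- Section 7.12, IT item 3, lists the same ground for stopping IT: "If the patient does not meet the criteria to start the next cycle within 21 days after the planned subsequent cycle start date".

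**The concern.** The stem of item 26 says how (a) and (b) combine. It does not say how the two enzymes inside (a) combine. A site that takes 'and' at face value needs both ALT and AST above 5 × UNL before the criterion applies. Another site may read the same line as one limit shared by two tests, so that either is enough.

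This matters because 26a is the only transaminase threshold in the protocol. It decides who may enter, and then whether a patient may start each further cycle, with up to 18 IT cycles foreseen in Section 7.2.1. On the literal reading, a child with a marked rise in one enzyme and acceptable bilirubin meets the written conditions for dosing. Two sites could also act differently on the same result at a cycle start.

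**Working it through.** There is no stated figure to reproduce. The check is one of text and logic.

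**1. Where the two readings differ.** Take bilirubin at or below 1.5 × UNL, so that 26b is silent. Each enzyme is either above 5 × UNL or not, giving 2 × 2 = 4 patterns.

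| ALT > 5 × UNL | AST > 5 × UNL | 26a met if both are needed | 26a met if either is enough |
|---|---|---|---|
| no | no | no | no |
| yes | no | no | **yes** |
| no | yes | no | **yes** |
| yes | yes | yes | yes |

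The criterion is met in 1 pattern under 'both' and 3 under 'either', so the readings disagree on 3 − 1 = 2. As an illustration with assumed values, take ALT at 8 × UNL, AST at 3 × UNL and normal bilirubin. Under 'both' the patient may enter or start the cycle; under 'either' the patient may not. If bilirubin is above 1.5 × UNL, item 26b decides and the readings give the same result.

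**2. Where the difference acts.** It acts at entry (Section 7.11.2) and at each cycle start (Section 8.1.1). The IT stop in Section 8.4.4.1 and Section 7.12, IT item 3, is not a separate point of application: it follows when the cycle-start criteria stay unmet for 21 days.

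**3. Whether another rule sets a level.**

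- Section 7.12 has 12 general + 6 IT + 2 GM-CSF = 20 discontinuation items. None names ALT or AST. IT item 3 reaches them only through item 26.
- Section 8.4.4.2 gives dose rules for diarrhea, for nausea and vomiting, and for dehydration, with none for liver enzymes.
- Sections 8.4.5 and 8.4.6, on naxitamab and GM-CSF reactions, contain no hepatic rule.
- Table 9 and Table 14 schedule ALT and AST without an action limit.

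**4. What the text suggests about intent.**

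- For 'either': the other laboratory limits in items 25 to 27 are 25a to 25d (4), 26b (1) and 27 (1). That makes 6, and each excludes alone. A lone limit needing two results would be out of pattern.
- For 'both': exclusion 13, in the same list, uses a different connector: "room air pulse oximetry < 94% and/or abnormal pulmonary function tests if these assessments are clinically indicated". A site could conclude that a plain 'and' was chosen on purpose. This is weak evidence, because connectors are used loosely elsewhere. In Section 8.4.6 the rule for resuming GM-CSF says 'and/or' of WBC and ANC. Taken as 'either', it would allow a restart while one count was still above its hold limit. The notes to Tables 9 and 14 use plain 'or' for the same two counts.

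On balance the structure favours 'either', but no sentence states it.

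**5. Which safeguards remain under the literal reading.**

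| Provision | Sets an ALT/AST level? | Requires exclusion or a hold? |
|---|---|---|
| Sponsor approval of eligibility before IMP (7.11) | no; works from the same criteria | no, for a single-enzyme rise |
| Postponement for IT toxicity, up to 21 days (8.1.3; Table 1, footnote 3) | no | no, permitted only |
| Schedule change: "Minor adjustment of the treatment schedule due to medical circumstances (e.g., infection) at the discretion of the investigator" (8.1.3) | no | no, permitted only |
| Bilirubin limit (26b) | no | yes, but on bilirubin |
| Repeat liver tests, including before each cycle and on Day 8 (Table 9) | no | no |
| Stop of all IMPs: "The investigator judges it necessary for medical reasons/non-compliance" (7.12, general item 8) | no | only if the investigator so judges |

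Exclusion 29 does not fill the gap. It is confined to illness that has nothing to do with the cancer or its treatment, so it would not catch a rise caused by treatment.

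**The case against.** The best reply is that the natural reading is two tests sharing one limit, that the structure of items 25 to 27 supports this, and that clinicians would apply it so. At entry, one sponsor reviews every eligibility form, which makes differences between sites less likely there. At later cycles, Section 8.1.3 lets a site postpone for IT toxicity without naming any laboratory threshold, so a single-enzyme rise judged to be IT toxicity can be held under either reading. Bilirubin is a separate limit, and liver tests are repeated.

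Most of this stands, and it rules out some stronger inferences. A reader might infer that the sponsor meant to require both enzymes; the documents do not show that, and the structure points the other way. A reader might infer that sites are unable to hold a cycle, or that no safeguard exists; the provisions just listed show otherwise. What survives is narrower. The hold is permitted but not required, the sponsor's review does not say which reading it uses, and no provision gives a level for ALT or AST. The point bears mainly on later cycle starts.

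**Conclusion.** The ambiguity is real and falls on an operative safety threshold. Read literally, 26a imposes no mandatory exclusion, cycle hold or IT stop when one enzyme exceeds 5 × UNL and bilirubin is at or below 1.5 × UNL. The readings part on two of four enzyme patterns. That is a count of patterns and says nothing about how often they occur. The documents give no rate of single-enzyme rises, so the number of patients affected cannot be estimated.

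The conclusion rests on the protocol text alone. Section 8.1 refers to the Investigator's Brochure and product summaries for further information; these were not available and may contain hepatic guidance. A reader might also infer that the primary result is at risk. The documents do not support that: the sample size, the power and the exact binomial test do not depend on this wording. It is a minor correction worth making for patient safety and consistency.

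**What to change.** Reword 26a to *ALT and/or AST > 5 times UNL*. Sections 8.1.1 and 8.4.4.1 refer back to Section 7.11.2 and inherit the change, as does Section 7.12, IT item 3, through them. If the sponsor did intend both enzymes, write *both ALT and AST* and state what a site should do at a cycle start when only one is above the limit.

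The edit is one word, but it is a protocol modification and needs approval under Section 14.3 before use, so it belongs in the next amendment. The possible cost is a few more screen failures, cycle delays or IT stops for a persistent rise in one enzyme. A patient who stops IT for toxicity can still be offered naxitamab with GM-CSF under Section 7.2.1. No change to the sample size or the analysis is needed.

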7.12 Premature Discontinuation of Treatment

General discontinuation criteria

A patient should be discontinued from treatment with all IMPs if any of the following situations occur:

1. Grade 4 anaphylaxis related to naxitamab
2. Grade 3 anaphylaxis related to naxitamab not responding to medical intervention at the discretion of the investigator
3. Grade 4 sensory neuropathy or Grade 3 sensory neuropathy that interferes with daily activities for more than 2 weeks at the discretion of the investigator
4. CTCAE Grade 3 pain unresponsive to maximum supportive measures at the discretion of the investigator
5. Grade 4 bronchospasm
6. Grade 3 bronchospasm not responding to medical intervention at the discretion of the investigator
7. Posterior reversible encephalopathy syndrome (PRES)
8. The investigator judges it necessary for medical reasons/non-compliance
9. The patient receives prohibited therapy and/or procedures during the trial, see Section [8.4.8](#)
10. Pregnancy
11. Patient/legal guardian withdraw consent to treatment
12. PD

Discontinuation criteria for IT

A patient should be discontinued from IT treatment if any of the following situations occur:

1. If the patient experiences neutropenia that causes a delay \geq 14 days after the first dose reduction by 20% of irinotecan and the second dose reduction by 20% of temozolomide
2. If the patient experiences thrombocytopenia that causes a delay \geq 14 days after the first dose reduction by 20% of irinotecan and the second dose reduction by 20% of temozolomide
3. If the patient does not meet the criteria to start the next cycle within 21 days after the planned subsequent cycle start date
4. Recurrence of \geq Grade 3 diarrhea despite maximal use of anti-diarrheals, prophylactic antibiotics, and a dose reductions of irinotecan of 20%
5. Recurrence of \geq Grade 3 regimen-related nausea and/or vomiting despite optimization of anti-emetic drugs and a dose reduction of IT by 20%
6. If \geq Grade 3 regimen-related dehydration recurs and persists for >3 days despite a dose reduction of IT by 20%

Discontinuation criteria for GM-CSF

A patient should be discontinued from GM-CSF treatment if any of the following situations occur:

1. Injection site reactions \geq CTCAE Grade 3
2. Allergic reactions (including anaphylactic reactions) \geq CTCAE Grade 3

For patients discontinuing all IMP treatments due to PD or toxicity as described above, the patient should attend the EOT visit (see Section 3) and subsequent enter long-term follow-up (see Section 7.8).

